Efficacy of vestibular rehabilitation using computerized dynamic posturography with virtual reality for stable unilateral vestibular weakness

Version 1.2

July 17, 2021

PI: [name]
Co-investigators: [name]

Lay Summary

People that have difficulty with balance, such as those with damage to their inner ear, have a higher risk of falling, which may lead to anxiety and reduced quality of life. Some individuals that have lost part of their sense of balance can learn to compensate using information from their vision, their sense of where their limbs are in space, and from other balance organs that are still intact. Our study aims to determine if virtual reality used together with information from footplate sensors can be used to train people with balance problems to compensate for their inner ear deficits.

Background

Vestibular dysfunction is common, with a reported prevalence of over 5% in children(1) and adults(2). In individuals with no equilibrium deficits, balance is maintained by integration of information from vision, somatosensory input, and from the vestibular sensors of the inner ear. Deficits in this system lead to imbalance symptoms, which adversely affect quality of life(3) and are associated with unemployment and poorer quality of life.(4) While most individuals with unilateral vestibular weakness are able to recover some of their balance function, either spontaneously or through rehabilitation, others suffer from persistent dizziness symptoms that are refractory to common rehabilitation approaches.(5)

Two technological advancements may provide a new mode of treatment for such people. The first, virtual reality (VR) has shown promise for rehabilitation of vestibular and mobility deficits.(6) The second, computerized dynamic posturography (CDP), analyzes posture, balance, and sway of the subject using a force plates beneath their feet.(7) Together, these technologies allow for detailed assessment and tailored, interactive compensatory rehabilitation with quantitative measurement of the subject's responses over time.

VR and CDP allow for the controlled quantitative measurement of responses to rehabilitation treatment; however, they may not capture the qualitative changes that reflect improvements in the patient's quality of life and functional capacity. Therefore, it is important to demonstrate

that any quantitative improvement measured by CDP translates to the patient-reported outcomes of increased activity, improved confidence, and reduced fear of falling.(8)

Hypotheses

VR-CDP-based rehabilitation will improve balance performance, as measured by Sensory Organization Test (SOT) scores, for individuals with unilateral vestibular loss.

VR-CDP-based rehabilitation interventions will improve patient-reported vestibular function.

Patients with unilateral vestibular weakness will consent to enrolment, will complete the initial, the post-intervention, and two follow-up assessments, and will successfully complete the prescribed course of 12 rehabilitation sessions.

Justification

Vestibular loss can be a major contributor to morbidity and loss of quality of life, increasing the risk of falls and leading to a reduction or avoidance of activity.(8) Many patients with unilateral vestibular loss report persistent symptoms of dizziness and imbalance despite rehabilitative attempts. Currently, the most common treatment available to such patients are static physiotherapeutic exercises which have not been consistently clinically validated by objective outcomes. The current treatment modalities are limited with respect to targeted therapies for each of the five discreet vestibular end organs, as well and functional outcomes. VR with CDP may offer a more effective and targeted means of promoting global balance compensation to improve the symptoms of dizziness caused by a specific inner ear deficiency in these individuals. However, the efficacy of this type of technology has not been established in the literature and the details of the intervention and the number of sessions required to confer improvement are unknown.

Objectives

Primary objective: To evaluate the efficacy of vestibular rehabilitation therapy using computerized dynamic posturography (CDP) with interactive visual feedback for the amelioration of long-standing imbalance in patients with peripheral unilateral vestibular weakness.

Secondary objectives:

- 1) To determine the variances (or standard deviations), means, and correlations in order to design a larger study with sufficient statistical power to compare the IVR-CDP intervention with standard care.
- 2) To estimate numbers of eligible patients and rates of consent for enrolment.
- 3) To estimate rates of adherence to the study protocol; specifically, (a) the percentage of patients that complete the full course of treatment, (b) complete the initial and follow up measures and (c) the number of missed or rescheduled visits, and (d) the rate of withdrawal from the study.

- 4) To determine performance scores for the individual exercises within the rehabilitation program, to ensure the difficulty is well-matched to patients' abilities.
- 5) To evaluate the durability, at 6 weeks and 3 months post-intervention, of any changes in:
 - a) Patient-reported vestibular symptoms (as measured by questionnaires);
 - b) Objective measures of imbalance (SOT and LOS tests).

Research Design

Study type: Longitudinal cohort; single group assignment; interventional

Intervention: 2x per week for 6 weeks of rehabilitation therapy

Study population

Adults (18-80 years of age) with stable unilateral vestibular weakness.

Recruitment

Subjects previously seen in the Principal Investigators clinic for unilateral vestibular weakness will be contacted and invited to enrol. We hope to enroll 25 subjects as a convenience sample for this single centre study.

Inclusion criteria

- Adult Age 18-80
- Unilateral vestibular weakness confirmed one or more of:
 - Videonystagmography
 - VEMP
- Or unilateral vestibular weakness idiopathic, not yet diagnosed (NYD)
- Persistent imbalance following diagnosis of resolved benign paroxysmal positional vertigo (BPPV)
- Symptomatic
- Long-standing/persistent symptoms greater than one year

Exclusion criteria

- Orthopedic deficit (eg. lower body joint dysfunction or lower joint replacement)
- Neurological deficit or proprioception deficit
- Diabetes
- Poor vision or blindness
- Fluctuating vestibular symptoms, or condition known to fluctuate eg. Menière's disease, perilymphatic fistula (PLF) or superior canal dehiscence (SDCS)
- Active benign paroxysmal positional vertigo (BPPV)
- Undergoing treatment which may affect balance or ability to stand
- Cognitive impairment that prevents understanding and responding to instructions required to complete the study
- Inability to provide informed consent

Study Procedures

Study data will be collected during visit 1 and 14, with two additional follow up visits at 6 weeks (visit 15) and 3 months (visit 16) post-intervention:

1) Validated questionnaires

- a) Dizziness Handicap Inventory (DHI)(9)
- b) Falls Efficacy Scale-International (FES-I)(10)
- c) Activities-specific Balance Confidence (ABC) scale(11)

2) Quantitative posturography assessment

- a) Sensory organization test (SOT)
- b) Limits of Stability (LOS) test

During all visits, a CDP instrument supplemented with interactive visuals will be employed to measure the subjects postural stability. Participants will stand on the instrument's platform and will view the prescribed interactive visuals. They will be prompted to either maintain stable equilibrium or to modulate their COG in response to the interactive visuals, as required for the SOT and LOS tests, respectively.

Details of the SOT Test (Visits 1, 14, 15 and 16)

The SOT has been widely used for research of postural stability for over 30 years.(12) This purpose of this test is to assess the competency of the subject's three modes of sensing equilibrium: vision, proprioception, and vestibular/inner ear sensors.

The SOT consists of 6 conditions, during which the subject will try to maintain their equilibrium. Each trial takes 20 seconds to perform, and each is performed in triplicate for a total of 18 trials. These 6 conditions test the three inputs to the subjects sense of equilibrium: vision, somatosensory, and vestibular. By having the subject close their eyes, by allowing the footplate to change in pitch, or by altering the visual stimulus, each of these inputs can be tested alone and in combination with the others.

The 6 conditions are: (1) eyes open, stable support; (2) eyes closed, stable support; (3) sway-referenced vision, stable support; (4) eyes open, sway-referenced support; (5) eyes closed, sway-referenced support; and (6) eyes open, sway-referenced vision, and sway-referenced support.

Each condition is given a score out of 100 and a composite score is calculated by the software

Details of the LOS test (Visits 1, 14, 15 and 16)

The purpose of this test is to determine the distance that the patient is able to voluntarily displace their center of pressure in different directions without losing balance.

Subjects will stand on the CDP platform with the arms at their sides. The test involves moving a pictogram, which represents their COG, to targets indicated on the visual display. There are eight targets distributed around the subject and the subject's performance in modulating their COG to meet the targets will be measured by software.

Study Intervention

Details of the rehabilitation exercises (Visits 2 to 13)

The rehabilitation exercises will employ the CDP instrument and visual feedback. Subjects will perform a series of exercises in which they will have to modulate their centre of gravity (COG), by shifting their weight side-to-side or front-to-back. By shifting their weight, subjects will direct a pictogram representing their COG to targets presented on the interactive display. All patients will receive the same series of exercises, except to account for the side, right or left, of the vestibular deficit (ie. the exercises for someone with a deficit on their right side will be a mirror image relative to someone with a deficit on their left side).

Over the course of the 12 sessions, the exercises presented to the subjects will become progressively more difficult in order to promote global balance improvement by brain, proprioceptive, visual, and vestibular compensation.

Study Schedule

Visit 1 (75 minutes) – Initial assessment

- Obtain written informed consent
- Verbal health check, any illness/injury that might affect performance?
- Questionnaires that measure disability caused by imbalance and risk of falling
 - Dizziness Handicap Inventory (DHI)
 - Falls Efficacy Scale-International (FES-I)
 - Activity-specific Balance Confidence Scale (ABC scale)
- CDP assessment
 - Sensory organization test (SOT)
 - Limits of Stability (LOS) test

Visit 2-13 (45 minutes) – Rehabilitation exercise

- Verbal health check, any illness/injury that might affect performance?
- Rehabilitation exercises

Visit 14-16 (75 minutes) – Post-intervention assessment and follow up

- Verbal health check, any illness/injury that might affect performance?
- Questionnaires that measure disability caused by imbalance and risk of falling
 - Dizziness Handicap Inventory (DHI)
 - Falls Efficacy Scale-International (FES-I)
 - Activity-specific Balance Confidence Scale (ABC scale)
- CDP assessment
 - Sensory organization test (SOT)
 - Limits of Stability (LOS) test

Safety

When the participants are using the CDP instrument, both for assessment and rehabilitation, they will be secured by a harness at all times to prevent falls. Participants will be informed that they may stop the testing or training or withdraw from the study at any time.

Time to participate

This study will involve 16 biweekly visits to the clinic. Sessions 1, 14, 15 and 16 are expected to take 75 minutes. The 12 rehabilitation sessions are expected to take 45 minutes. In total, the time to participate for the entire study is estimated to be 13 hours. The rehabilitation sessions will take place over a period of approximately 7 weeks with addition follow up visits at 6 weeks and 3 months after the post-intervention assessment.

Missed sessions

Missed sessions will be rescheduled so that subjects may complete the full course of 12 sessions. Subjects that have not completed the full 12 sessions by 10 weeks after their first visit will be scheduled for the post-intervention assessment. Subjects that have not completed the post-intervention assessments within 12 weeks will be excluded from further data collection and analysis.

Follow up sessions will be schedule for 6 weeks (+/- 1 week) and 3 months (+/- 2 weeks) after the post-intervention assessment (visit 14).

Study data and measurements

Demographic and medical history

Demographic and medical history data will be extracted from the patient charts. Data will be recorded in a Microsoft Excel database designed for this purpose. The PI will monitor the study and perform quality controls of the entered data and ensure the subject's privacy and rights are protected.

Demographic

- Age
- Gender

Vestibular screening or medical history

- Vestibular diagnosis
- Result of tests
 - cVEMP
 - oVEMP
 - vHIT
 - Caloric response

Outcome measurements

Each of the following will be measured during visits **1, 14, 15 and 16**

1. Sensory organization test (SOT) composite score;
2. Mean value of CDP SOT conditions 1 through 6: calculated by software;

3. CDP SOT vestibular contribution value: (mean value of condition 5/mean value of condition 1) × 100;
4. Mean value of directional control of limits of stability in CDP: calculated by software;
5. Mean endpoint excursion value and maximum excursion point of limits of stability in CDP: calculated by software;
6. Dizziness handicap inventory (DHI) score
7. FES-I score
8. Activity-specific Balance Confidence Scale

Statistical analysis

We will enrol a convenience sample of patients previously seen in the Principal Investigator's clinic in order to collect preliminary efficacy data and assess the feasibility of a larger trial.

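### Secondary objective 2 asks for the number eligible and the consent rate, but a convenience sample of 25 with no defined frame, contact order or denominator need not yield either for the clinic.

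*Combined protocol and SAP*

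**What the plan says.** Under Objectives, secondary objective 2 reads "To estimate numbers of eligible patients and rates of consent for enrolment". The Hypotheses section adds the expectation that "Patients with unilateral vestibular weakness will consent to enrolment", with no target rate.

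The Recruitment section names the source: "Subjects previously seen in the Principal Investigators clinic for unilateral vestibular weakness will be contacted and invited to enrol". It continues: "We hope to enroll 25 subjects as a convenience sample for this single centre study". The Statistical analysis section repeats the method ("We will enrol a convenience sample of patients previously seen in the Principal Investigator's clinic") and gives its purpose as preliminary efficacy data and the feasibility of a larger trial.

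The plan does not say whether all former patients, a consecutive series or only some of them will be contacted, over what period, or in what order. It provides no log of patients screened, eligible, approached or declining, and it does not define the denominator of the consent rate. The list under Outcome measurements contains no eligibility or consent measure. The only analysis text that could apply is the general statement that categorical variables will be summarised as percentages of subjects.

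**The concern.** Counting eligible patients and estimating the share who consent both need a defined set of people who were screened and approached. A convenience sample supplies no such set unless something further is specified. If contact stops once 25 have enrolled, eligible patients not yet reached need never be counted. Those who were contacted may also differ from the rest in their willingness to take part. A log of calls would then give a correct rate among those called, but not the clinic's rate.

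What is at stake is the feasibility reading. The Statistical analysis section ties this sample to judging whether a larger trial is feasible, and the number eligible and the consent rate are natural inputs to that judgement. There is a second limit on carrying the rate forward. This study is described as "Study type: Longitudinal cohort; single group assignment; interventional", so everyone who consents receives the intervention. The later study is meant to compare the intervention with standard care, and willingness to join that may differ.

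**Working it through.** **No figure to reproduce.** The plan gives 25 as a target. It states no expected consent rate, number eligible or number to be approached. What follows is an illustration.

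**Inputs**
- From the Recruitment section: 25 enrolled, taken here as 25 consents.
- Assumed: 62 eligible patients at the clinic, 40 of them contacted, and a later trial of 120.

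**Step 1. Observed rate among those contacted.** 25/40 = 62.5%. The exact (Clopper-Pearson) 95% CI is 45.8% to 77.3%. This interval covers sampling error only, and only if the 40 can be treated as representative.

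**Step 2. Bounds for the rate among all eligible.** The number not contacted is 62 − 40 = 22.
- If all 22 would refuse: 25/62 = 40.3%.
- If all 22 would consent: (25 + 22)/62 = 47/62 = 75.8%.
- If half would consent: (25 + 11)/62 = 36/62 = 58.1%.

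The bounds lie on both sides of 62.5%, so the sampling method alone does not fix the direction of the error.

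**Step 3. Consequence for a later trial of 120.** Approaches needed = 120 / consent rate.
- Planned from the observed rate: 120/0.625 = 192.
- At the lower bound: 120 × 62/25 = 297.6, about 298.
- At the upper bound: 120 × 62/47 = 158.3, about 158.
- At the midpoint case: 120 × 62/36 = 206.7, about 207.

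**Step 4. Sensitivity to the number not contacted.** Keep 40 contacted and 25 consenting.
- With 50 eligible, the bounds are 25/50 = 50% and (25 + 10)/50 = 70%.
- With 100 eligible, they are 25/100 = 25% and (25 + 60)/100 = 85%.

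The range widens with the share of eligible patients never approached, and closes to a single value when all are approached. Under the plan as written, that share would not be known.

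**Step 5. Interval when recruitment stops at 25 consents.** With the number of consents fixed and the number contacted random, the exact upper limit for 25 out of 40 is 76.6% instead of 77.3%, and the lower limit stays at 45.8%. The difference is minor.

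**The case against.** The strongest reply is that the plan does name a finite source population and says that its members will be contacted and invited. Read this way, convenience sample may mean only that one accessible clinic is used and that 25 was not derived from a power calculation. The whole list could be screened and logged without departing from the text. That is a fair reading, and it means that a usable denominator is undefined in the plan but not ruled out by it.

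A reader might infer more: that staff will hand-pick willing patients, that no valid denominator can exist, or that the consent rate will be overstated. The documents support none of these. Selective calling is nowhere stated. Consented over contacted is a valid rate for those contacted; what is open is how far it generalises. The bounds above allow error in either direction, and the 40% end requires every uncontacted patient to refuse. If half would consent, the gap is small (207 approaches against 192).

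Nor do the documents say that these rates will set the size or timing of the larger trial. Objective 1 supplies the variances, means and correlations for power; objective 2 states no use, and the Statistical analysis section speaks only of feasibility.

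The remaining point stands. The reading that rescues the objective is one in which the full list or a consecutive series is screened and logged. The plan does not commit to that, and following its text as written need not produce it.

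**Conclusion.** The concern holds as a mismatch between a stated objective and a stated sampling method. As planned, the number eligible may not be obtained, and the consent rate would apply only to the patients contacted. It may overstate or understate the clinic's rate. Overstatement is a risk if likely acceptors are called first; it is not an established bias.

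On the assumed figures (62 eligible, 40 contacted, 25 consenting), an observed 62.5% is compatible with 40% to 76% among all eligible, and a plan of 192 approaches for an assumed trial of 120 with a need of about 158 to 298. The actual size depends on how many eligible patients go uncontacted and how they differ from the others, neither of which the documents give.

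This affects a descriptive secondary objective and leaves the primary efficacy analysis untouched. It should still be settled before the first call, because the order of contact and the patients passed over may not be recoverable later.

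**What to change.** In the Recruitment and Statistical analysis sections, replace the convenience sample with a consecutive or randomly ordered sample:

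1. Before the first call, list all patients seen in the clinic for unilateral vestibular weakness in a fixed date window.
2. Check every chart on the list against the inclusion and exclusion criteria, so that the number eligible is known even if enrolment ends early.
3. Contact eligible patients in list order or random order until 25 are enrolled.
4. Log the numbers identified, eligible, contacted, reached and consented, with reasons for refusal.
5. Report eligible/identified and consented/contacted with 95% CIs. For the consent rate, use an interval that allows for stopping at 25 consents.
6. State that the inference is limited to this clinic and to consent for a single-group study. Better sampling does not remove that limit, since the aim is to "design a larger study with sufficient statistical power to compare the IVR-CDP intervention with standard care".

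Cost: some hours of chart review on a list the site has to consult anyway, and possibly slightly slower recruitment. No extra patients or study procedures are needed.

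### Does the resolved-BPPV inclusion bullet open the trial to people without unilateral vestibular weakness?

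*Combined protocol and SAP*

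**What the plan says.** The Inclusion criteria give, in order: age; unilateral weakness shown on videonystagmography or VEMP; "Or unilateral vestibular weakness idiopathic, not yet diagnosed (NYD"); "Persistent imbalance following diagnosis of resolved benign paroxysmal positional vertigo (BPPV"); being symptomatic; and symptoms lasting more than a year. Only the idiopathic bullet is marked as an alternative. The Exclusion criteria bar "Active benign paroxysmal positional vertigo (BPPV").

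Other sections describe the population in one way. Study population has "Adults (18-80 years of age) with stable unilateral vestibular weakness". Recruitment says "Subjects previously seen in the Principal Investigators clinic for unilateral vestibular weakness will be contacted and invited to enrol". The primary objective concerns "amelioration of long-standing imbalance in patients with peripheral unilateral vestibular weakness". Under Details of the rehabilitation exercises, everyone receives the same series "except to account for the side, right or left, of the vestibular deficit".

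One secondary objective is "To estimate numbers of eligible patients and rates of consent for enrolment"; another is to obtain means and standard deviations for designing a larger study. The section on demographic and medical history extracts vestibular diagnosis and the cVEMP, oVEMP, vHIT and caloric results. Statistical analysis plans descriptive summaries and a paired Wilcoxon signed-rank comparison of initial with post-intervention scores, with no breakdown by diagnosis or route of entry.

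**The concern.** The resolved-BPPV bullet names neither unilateral weakness nor a side, and nothing says how it combines with the rest of the list. Because it follows directly on a bullet that opens with an alternative, a screener could take it as a further alternative. Someone with lingering imbalance after BPPV could then enter without any criterion requiring unilateral weakness.

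Three things would be at stake. The before-and-after result, and the means and standard deviations meant for the larger trial, could describe a mixed group while being reported as findings in unilateral weakness. The count of eligible patients, itself an objective, would depend on how the bullet was read. And the mirroring rule would be undefined for a subject with no identified side.

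**Working it through.** The protocol gives no figure to reproduce: the 25 subjects are a convenience sample, with no power calculation behind them. The check is to set each reading of the bullet against the other sections.

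| Reading | Title, primary objective, Study population | Recruitment source | Side rule for exercises |
|---|---|---|---|
| Required of everyone | Restricts the trial to post-BPPV patients, which none of them says | Not mentioned there | Works, since weakness is also required |
| Alternative to weakness | Conflicts: weakness not required | Limits it: those contacted were seen for unilateral weakness | Undefined if no side is recorded |
| Permitted alongside weakness | Fits | Fits | Works |

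1. *Required.* Every subject would need a past BPPV diagnosis. No objective, hypothesis or population statement supports this.

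2. *Alternative.* This is the only reading that produces the mixed group. The Recruitment section narrows it in practice, because the people approached are those already seen for unilateral weakness, and the idiopathic bullet already takes in unilateral weakness of unknown cause. Few subjects, if any, could enter through the BPPV bullet alone. The side rule is undefined for such a subject but not necessarily unusable: it refers to the side of the vestibular deficit, and a patient with past BPPV may have a recorded side, although the protocol does not require one.

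3. *Permitted.* Active BPPV is excluded, so a line making clear that resolved BPPV is no bar is a natural counterpart. It agrees with every other section.

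**Size.** Each subject without unilateral weakness would be 1/25 = 0.04, or 4% of planned enrolment. The protocol gives no share of subjects by route of entry, so no shift in the mean change or its standard deviation can be calculated.

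**Effect on the analysis.** There is one group and each subject is compared with their own baseline. A mixed intake cannot create an imbalance between arms; it changes only whom the result describes. Diagnosis and vestibular test results are collected, and percentages are planned for categorical variables, so a report would largely show who had unilateral weakness. Side is not a listed data field, but staff must know it to set up the mirrored exercises.

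**The case for a change.** The strongest argument for a change is that the permissive reading makes the bullet redundant. Excluding active BPPV already leaves resolved BPPV admissible, so a reader who expects each inclusion bullet to do some work will lean towards the alternative reading. In addition, Recruitment describes whom to contact, not who is eligible, and Statistical analysis restates the source as earlier patients of the clinic without mentioning weakness. On this view, an objective that counts eligible patients rests on an undefined criterion, and a few words would cure it.

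Part of this stands. The text does not settle the logic, and the redundancy argument is fair. It does not amount to a flaw in the plan, however. A redundant reassurance in an eligibility list is harmless, whereas the alternative reading contradicts the title, the primary objective and the Study population statement. The sentence in Statistical analysis reads as a shortened restatement of Recruitment, not a second source of patients. With a single centre drawing on the principal investigator's own patients, different sites cannot apply different readings, and the eligible count can be reported together with the rule used in screening. A planned analysis by route of entry would matter only if the bullet were an alternative and such subjects also enrolled. The protocol establishes neither, and in a preliminary study of 25 the omission is not an error.

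**Conclusion.** The ambiguity is real but minor: a missing connecting word in a list whose intended population is stated consistently elsewhere. The effect on results is small and possibly nil, at 4% of the planned sample for each subject without unilateral weakness, with none shown to be likely. No test, error rate or sample size changes.

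This rests on two assumptions: that screening follows the Study population statement, and that recruitment stays with patients seen for unilateral weakness. If subjects without it did enrol, the recorded diagnoses and test results would largely identify them, and a sensible analyst would describe the sample accordingly. How the bullets combine, and who is eligible, are for the investigators to settle, keeping the list consistent with the Study population statement and the side rule. That is ordinary clarification of wording, and it does not call for a change to the design or the analysis.

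### The 12-week cut-off for visit 14 ends all later assessment and analysis, even for a fully trained and willing participant, so data that could still be collected are given up

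*Combined protocol and SAP*

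**What the plan says.** Two sentences in Missed sessions govern late participants. The first is about training: "Subjects that have not completed the full 12 sessions by 10 weeks after their first visit will be scheduled for the post-intervention assessment". The second is about assessment: "Subjects that have not completed the post-intervention assessments within 12 weeks will be excluded from further data collection and analysis". The second has no exception for a participant who completed training, and it does not state when the 12 weeks begin. The sentence before it suggests the first visit.

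The same section sets visits 15 and 16 at "6 weeks (+/- 1 week) and 3 months (+/- 2 weeks) after the post-intervention assessment (visit 14"), and Time to participate also counts them from that assessment. Secondary objective 5 is "To evaluate the durability, at 6 weeks and 3 months post-intervention, of any changes in" symptoms and balance measures. Study Procedures likewise places these visits relative to the intervention.

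The Statistical analysis section plans descriptive summaries and a paired Wilcoxon signed-rank test of initial against post-intervention scores. It defines no analysis set, no handling of missing data and no sensitivity analysis. On size, Recruitment says: "We hope to enroll 25 subjects as a convenience sample for this single centre study".

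**The concern.** The rule selects on something that happens after baseline, namely being assessed by a given date, and not on whether a measurement can be had. It also stops collection, not only analysis. A late score can be set aside later, but a score never taken cannot be recovered.

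Three uses of the data are exposed. They are the before-after change (primary objective), durability (secondary objective 5), and the means, standard deviations and correlations meant for designing the larger trial (secondary objective 1). With one group and no control, nothing offsets a selective loss. If those cut off improved less than those kept, all three would look too favourable.

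**Working it through.** **1. Schedule.** Research Design gives "2x per week for 6 weeks of rehabilitation therapy". Visits 1 to 14 at two per week take 14 / 2 = 7 weeks, which agrees with "The rehabilitation sessions will take place over a period of approximately 7 weeks". Slack to the cut-off is 12 − 7 = 5 weeks for someone on schedule, and 12 − 10 = 2 weeks for someone sent to visit 14 at week 10.

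**2. Who is kept and who is dropped**, counting from the first visit:

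| Training | Visit 14 | Weeks since training | Under the rule |
|---|---|---|---|
| few sessions, sent at week 10 | week 10 | varies | kept |
| all 12, ends about week 7 | week 12 | about 5 | kept |
| all 12, ends about week 7 | a day after week 12 | about 5 | dropped |
| continues to week 10 | a day after week 12 | about 2 | dropped |

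The rule tracks neither the amount of training nor the interval since training. The second row is kept at about 5 weeks after training, while the fourth is dropped at about 2.

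**3. What is lost.** Outcomes are measured at visits 1, 14, 15 and 16. A dropped participant keeps only visit 1, so up to 4 − 1 = 3 assessments go, and with them the paired difference and both durability values.

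**4. Calendar of the others.** Taking 3 months as 13 weeks, a participant with visit 14 at week 7 has visit 15 at weeks 7 + 5 to 7 + 7 = 12 to 14, and visit 16 at weeks 7 + 11 to 7 + 15 = 18 to 22. On-schedule participants are therefore still being assessed after week 12.

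**5. Illustration of bias.** The documents give no SOT gain and no exclusion rate, so every input except 25 is assumed. Let those kept gain 10 points, and let k of 25 be cut off but measurable, with gain g. The mean over all 25 is [(25 − k) × 10 + k × g] / 25.

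| k | g | Mean over all 25 | Reported 10 is |
|---|---|---|---|
| 2 | 0 | 9.2 | 9% too high |
| 4 | 0 | 8.4 | 19% too high |
| 6 | 0 | 7.6 | 32% too high |
| 4 | 5 | 9.2 | 9% too high |
| 4 | 10 | 10.0 | unbiased |
| 4 | 15 | 10.8 | 7% too low |

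**6. Illustration of precision.** Each participant lost is 1/25 = 4% of the sample. The protocol makes no power claim. With an assumed standardised paired effect of 0.5, two-sided 0.05, and the approximation Φ(0.5 × √(n × 3/π) − 1.96), power is 0.685 with 25 pairs, 0.668 with 24 and 0.589 with 20.

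**The case against.** *Some limit on visit 14 is legitimate.* A score taken 5 to 6 weeks after training measures retention more than immediate effect, and it falls where the 6-week follow-up is meant to look. That stands, and the fix has to handle it. It does not justify this rule, which runs from entry and already keeps a visit 14 about 5 weeks after training.

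*The rule will seldom apply.* This also stands. A reader might infer that anyone late for visit 14, or anyone who misses sessions, is excluded. The text does not say so: late means past week 12, and the week-10 sentence means that missed sessions alone exclude nobody.

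*The data may not be obtainable.* Some participants past week 12 will have dropped out for good, and no wording recovers them. The point concerns only those still willing to attend.

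*Visits 15 and 16 have another anchor.* A reader might infer that they have none but visit 14. Study Procedures and secondary objective 5 place them after the intervention, so that goes too far. The operational text in Missed sessions nevertheless schedules them from visit 14 and stops collection outright.

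*There may be operational limits.* The documents state no study end date and no limits on staff or equipment. That others are seen to weeks 18 to 22 shows only that the clinic is still assessing then. It does not show that open-ended visits are feasible, so the fix sets an upper limit.

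**Conclusion.** The point holds as a design weakness that should be corrected. A stated rule discards, on post-baseline behaviour, up to three of four assessments from participants who may be willing and fully trained, and nothing in the Statistical analysis section brings them back. This rests on the text alone, apart from reading the 12 weeks as running from the first visit.

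The size does not follow from the documents. A reader might infer that the reported change will be inflated because late participants are those doing poorly. The documents offer no support for that: lateness from travel or scheduling could leave the estimate unbiased, and lateness in people who feel better would push it the other way. The 32% figure needs 6 of 25 cut off, all measurable and all with no gain. Nor does the point depend on whether excluded participants also leave the adherence and withdrawal rates of secondary objective 3, which the text does not settle.

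For an uncontrolled convenience sample gathering preliminary data, the effect on conclusions is probably modest. The case for change is that the loss is avoidable at little cost.

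**What to change.** Replace the exclusion sentence in Missed sessions with:

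> Participants without visit 14 by 12 weeks after the first visit remain in the study unless they withdraw. Visit 14 is done at the earliest date they can attend, up to their visit 16 window. The dates of the last training session and of every assessment are recorded. If visit 14 is missed or done after week 12, visits 15 and 16 are timed at 6 weeks and 3 months from the last training session, with the existing windows; a late visit 14 that falls in one of those windows also serves as that follow-up visit. The first assessment after training is the post-intervention value in the paired test, flagged if after week 12. All participants with a baseline and the relevant later assessment are analysed. An analysis restricted to visit 14 within 12 weeks is reported as a sensitivity analysis.

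The fully trained participant seen just after week 12 then contributes a flagged value to the paired test and, about 5 weeks after training, the 6-week value as well. A late visit 14 no longer pushes visits 15 and 16 off their planned times. Anyone who attends no training session has no last-session date, so the sponsor should state an anchor for that case.

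The cost is protocol wording, date recording, a flag and one extra analysis. No procedure is added, and the training rules are untouched. The downside is small: a few post-intervention values will be taken at more variable times after training, which the flag and the restricted analysis make visible.
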